1. STUDY OBJECTIVE

To evaluate the ocular safety, tolerability, and efficacy of topical administration of SURF-201 (0.2% betamethasone sodium phosphate [BSP] ophthalmic solution) compared with vehicle when dosed twice daily (BID) for 1 day prior to cataract surgery, the day of cataract surgery, and 14 days post cataract surgery.

2. STUDY DESIGN

This study is a Phase 2, multicenter, randomized, double-masked, vehicle-controlled, parallel-group clinical trial. The investigator and his/her staff will not know which study medication the subject is receiving but will be able to determine this in the event of an emergency.

Prior to enrollment, the study will be discussed with prospective subjects and those wishing to enter will be asked to give written informed consent. Informed consent will be obtained prior to any study related procedures being performed. Once informed consent has been obtained, the subjects will be questioned regarding their medical history to determine whether or not they are in satisfactory health to enter the study and to determine if they meet the specific entry criteria.

During the screening phase (Day -2 to Day -14) of the study, subjects who meet all inclusion and none of the exclusion criteria will be randomized in a 1:1 ratio: 40 subjects in the 0.2% BSP group and 40 subjects in the vehicle group.

During the dosing phase (Day -1 to Day 14), subjects will dose BID for 16 days: the day before cataract surgery, the day of cataract surgery, and for 14 days after cataract surgery. Subjects will then be followed for approximately 2 weeks during the evaluation phase (Day 15 to Day 32).

There will be 7 study visits for full study participation: 1 visit during the screening phase, 3 visits (Day 0, Day 1 and Day 8) during the dosing phase, and 3 visits (Day 15, Day 22, and Day 32) during the evaluation phase.

Subjects will instill 3 doses of study drug prior to surgery (2 doses on Day -1, and 1 dose on Day 0 prior to surgery), 1 dose in the evening after surgery and continue dosing BID for 14 days after surgery.

Subject safety will be evaluated throughout the study. The safety parameters to be assessed are the incidence of adverse events (AEs) and serious adverse events (SAEs), discontinuations due to AEs, changes in visual acuity (VA) and intraocular pressure (IOP), and biomicroscopic and ophthalmoscopic findings.

Efficacy will be assessed by biomicroscopic measurement of anterior chamber cells (ACCs) and measurement of the subject's pain level at each visit using a visual analog scale (VAS). Subject pain will also be assessed by subjects at home using a subject diary.

All ratings and procedures should be performed by the same examiner from visit to visit whenever possible.

Additional exams may be scheduled as necessary to ensure the safety of the subjects during the study period.

3. STUDY CONDUCT

Initiation of this study requires acceptance and approval by a qualified, properly constituted Institutional Review Board (IRB). Approval of the study by the governing IRB will be secured prior to the initiation of the study at each site and a copy of the approval provided to the study Sponsor or designee. The IRB must function in compliance with 21 CFR, Part 56 of the US Food and Drug Administration's (FDA) Code of Federal Regulations (CFR).

This study will be conducted in compliance with the protocol approved by the IRB, and according to Good Clinical Practice (GCP) standards. No deviation from the protocol will be implemented without the prior review and approval of the IRB except where it may be necessary to eliminate an immediate hazard to a research subject. In such cases, the deviation will be reported, in writing, to the IRB and the Sponsor or designee as soon as possible.

4. STUDY POPULATION

Approximately 80 subjects, 18 years of age and older, who are scheduled to undergo uncomplicated unilateral cataract surgery (phacoemulsification or extracapsular extraction; surgery must not be performed with the aid of a femto [femtosecond] laser) and who meet all study entry criteria will participate in the study.

4.1. Inclusion Criteria

The following are inclusion criteria for prospective study subjects to be confirmed at Visit 1 (Day -14 – Day -2) prior to randomization.

1. Adult subjects, age 18 years or older, scheduled for uncomplicated unilateral cataract surgery (phacoemulsification or extracapsular extraction; surgery must not be performed with the aid of a femto [femtosecond] laser) with posterior chamber intraocular lens implantation.
2. Subjects must be able to understand and sign the Informed Consent Form (ICF).
3. Female subjects of childbearing potential must agree to and submit a negative urine pregnancy test before any study-specific procedures are performed. The subjects must be using and continue to use a suitable method of contraception for the duration of the study: spermicide with barrier, oral contraceptive, transdermal contraceptive, injectable or implantable contraceptive, intrauterine device (IUD), abstinence or surgical sterilization of a partner. If a subject is not of childbearing potential (e.g., has been postmenopausal for at least 12 months or is premenarchal, or has undergone a hysterectomy, bilateral oophorectomy or a bilateral tubal ligation), a urine pregnancy test and use of a suitable method of contraception for the duration of the study will not be required.

4. Subjects must have a best-corrected visual acuity (BCVA) of at least +1.0 log of the minimum angle of resolution (logMAR) (Snellen equivalent of 20/200) in the non-study eye (fellow eye).
5. Subjects must have an intraocular pressure (IOP) of >8 mmHg and ≤22 mmHg in the study eye (surgery eye).
6. Subject must agree to maintain their current dosing regimen throughout the study period (from Screening through Day 32) if they are currently using topical cyclosporin-A or Xiidra (lifitegrast 5%).
7. Subjects must be willing and able to attend all study visits and follow all instructions.
8. Subjects must be able to self-instill the study drug (if unable, a caregiver must be available to instill all doses of the study drug).
9. Subjects must agree to avoid any medications which are disallowed (as defined by the protocol).

4.2. Exclusion Criteria

The following are exclusion criteria for prospective study subjects to be confirmed from Day -14 – Day -2 (at Visit 1) prior to randomization:

1. Subject has any intraocular inflammation (cells and flare in the anterior chamber) or ocular pain (pain score of >0) in either eye prior to surgery.
2. Subject has any extraocular inflammation in the study eye prior to surgery (blepharitis is allowed if only scurf is present without any concurrent conjunctivitis or lid erythema/edema) or ongoing uveitis.
3. Subject has a history of diabetic retinopathy and/or previous vitrectomy in the study eye within the last 2 years prior to Screening which, in the investigator's opinion, is clinically significant and could impact the normal outcome of an uncomplicated cataract surgery.
4. Subject has a diagnosis of severe dry eye in the study eye.
5. Subject has any sign of iritis or scleritis in the study eye.
6. Subject has a history of glaucoma surgery in the study eye within the last 2 years prior to Screening.
7. Subject has a history of retinal surgery in the study eye within the last 2 years or plans to undergo retinal surgery in the study eye during the study period (from Screening through Day 32)

8. Subject has a history of Fuchs' dystrophy in the study eye.
9. Subject has guttata or chalazion in the study eye.
10. Subject has undergone radial keratotomy, photorefractive keratotomy, advanced surface ablation, corneal transplant, or LASIK in the study eye within the last 2 years prior to Screening.
11. Subject plans to undergo cataract surgery in the non-study (fellow) eye during the study period (from Screening through Day 32).
12. Subject plans to undergo additional ocular surgery (including femtosecond laser-assisted cataract surgery, minimally invasive glaucoma surgery, astigmatic keratotomy, limbal relaxing incision surgery, mechanical pupillary expanders, conjunctival incisions, and vitrectomy) in either eye during the study period (from Screening through Day 32).
13. Subject has a history of intraocular injections in the study eye within 6 months prior to Screening.
14. Subject has a history of herpes simplex infection in either eye.
15. Subject has active corneal, conjunctival or canalicular pathology (including ocular infection [bacterial, viral or fungal]) in the study eye. Specifically, active viral diseases of the cornea and conjunctiva including epithelial herpes simplex keratitis (dendritic keratitis), vaccinia, and varicella, and also in mycobacterial infection of the eye and fungal diseases of the ocular structures (such as fungal keratitis).
16. Subject has thinning of the cornea or sclera.
17. Subject plans to undergo uncomplicated unilateral cataract surgery with the aid of anterior capsular staining products (e.g., Trypan blue) or with the aid of a femto (femtosecond) laser.
18. Subject has undergone anti-neoplastic therapy within the last 2 years prior to Screening or plans to undergo anti-neoplastic therapy during the study period.
19. Subject has a history of use of medications to treat benign prostatic hyperplasia that, in the opinion of the investigator, limits adequate dilation of the pupil to safely perform uncomplicated cataract removal and IOL implantation.
20. Subject has a history of liver disease within the last 5 years prior to Screening.
21. Subject has a history of previous ocular trauma in the study eye that places the study eye at risk of increased post-surgical complications or inflammation.
22. Subject has or had a known blood dyscrasia or bone marrow suppression.

23. Subject has an active or chronic/recurrent ocular or systemic disease that is not controlled and may have an impact on wound healing (e.g., diabetes mellitus, systemic connective tissue disease, severe atopic disease).
24. Subject is suffering from alcohol and/or drug abuse.
25. Subject has a known hypersensitivity or poor tolerance to betamethasone and/or betamethasone sodium phosphate or any component of the study drug or any of the procedural medications such as anesthetic and/or fluorescein drops, dilating drops, etc.
26. Female subjects who are currently pregnant or nursing or are planning to become pregnant during the study or have a positive pregnancy test.
27. Subject has previously participated in this study protocol.
28. Subject used (within 30 days of initiation of study treatment) or is anticipating concurrent use of an investigational drug or device.
29. Subject has a condition or a situation which, in the investigator's opinion, might put the subject at increased risk, confound the study data or interfere significantly with the subject's study participation.
30. Subject would be wearing contact lens in either eye during the dosing period of Day -1 to Day 14.
31. Subject is taking a medication that the investigator feels might interfere with the study parameters.
32. Subject tests positive for the COVID-19 virus prior to Visit 1 (Day -14 to Day -2).

5. STUDY DRUG/INSTRUCTIONS FOR USE AND ADMINISTRATION

The study drug will be masked, packaged and labeled in a manner consistent with the study design. The Sponsor or designee shall provide the packaging of the study drug and the labeling of subject numbers according to a validated SAS® computer-generated randomization list. The study drug will be identified as a new drug, limited by Federal law to investigational use, manufactured and packaged for Surface Pharmaceuticals.

Subjects will be randomly assigned to receive masked study drug (either 0.2% BSP ophthalmic solution or vehicle) for 16 days BID. Subjects will receive instructions for dosing at home and for completing a dosing and pain assessment diary during the study dosing phase (Day -1 to Day 14).

During the 16-day dosing period, a total of 32 doses (2 doses each day, once in the morning and once in the evening, preferably 8-12 hours apart) will be instilled in the study eye by the subject (or their caregiver).

6. CONTRAINDICATIONS, WARNINGS AND PRECAUTIONS

Contraindications: Betamethasone sodium phosphate (BSP), as with other ophthalmic corticosteroids, is contraindicated in most active viral diseases of the cornea and conjunctiva including epithelial herpes simplex keratitis (dendritic keratitis), vaccinia, and varicella, and also in mycobacterial infection of the eye and fungal diseases of ocular structures.

Warnings and Precautions: Ocular adverse reactions which may occur with SURF-201 based on marketed ophthalmic corticosteroids include the following:

- Prolonged intensive use of corticosteroids may result in intraocular pressure (IOP) increase, glaucoma with damage to the optic nerve, posterior subcapsular cataracts, thinning of the globe and eventual perforation, secondary ocular infection, reduced visual acuity and visual field defects, mydriasis, ptosis, epithelial punctate keratitis, and corneal calcification may occur.
- Delayed healing - The use of steroids after cataract surgery may delay healing and increase the incidence of bleb formation. In those diseases causing thinning of the cornea or sclera, perforations have been known to occur with the use of topical steroids.
- Bacterial infections - Prolonged use of corticosteroids may suppress the host response and thus increase the hazard of secondary ocular infections. In acute purulent conditions, steroids may mask infection or enhance existing infection.
- Viral infections - Use of ocular steroids may prolong the course and may exacerbate the severity of many viral infections of the eye (including herpes simplex).
- Fungal infections - Fungal infections of the cornea are particularly prone to develop coincidentally with long-term local steroid application. Fungus invasion must be considered in any persistent corneal ulceration where a steroid has been used or is in use. Fungal culture should be taken when appropriate.

Special Warnings and Precautions for Use:

- Topical corticosteroids should never be given for an undiagnosed red eye as inappropriate use is potentially blinding.
- Persistent visual disturbance may be reported with systemic and topical corticosteroid use. Persistent symptoms such as blurred vision or other visual disturbances should be evaluated for possible causes which may include cataract, glaucoma or rare diseases such as central serous chorioretinopathy (CSCR) which have been reported after use of systemic and topical corticosteroids.

Undesirable Effects:

- Hypersensitivity reactions usually of the delayed type, leading to irritation, burning, stinging, itching and dermatitis.
- Corneal calcification has been reported very rarely in association with the use of phosphate-containing eye drops in some patients with significantly damaged corneas.

Overdose: Long term intensive topical use may lead to ocular corticosteroid specific class effects. Oral ingestion of the contents of a single-dose container of SURF-201 is unlikely to lead to any serious adverse effects.

Drug-Drug Interactions: No topical ophthalmic drug-drug interactions are known for SURF-201. Corticosteroids (including betamethasone) are metabolized by CYP3A4. Ketoconazole has been reported to decrease the metabolism of certain corticosteroids by up to 60%, leading to an increased risk of corticosteroid side effects. Coadministration with other strong CYP3A4 inhibitors (e.g. itraconazole, clarithromycin, ritonavir, cobicistat-containing products) may lead to increased exposures of corticosteroids and therefore the potential for increased risk of systemic corticosteroid side effects. (Celestone Soluspan PI, 2018).

Effects on Ability to Drive and Use Machines: SURF-201 may cause transient blurring of vision on instillation into the eye. Patients should be warned not to drive or operate hazardous machinery unless vision is clear.

7. CONCOMITANT MEDICATIONS

Disallowed medications include:

- Any corticosteroid at least 15 days before surgery and throughout the duration of the study;
- Depot-corticosteroids in either eye at least 45 days before surgery and throughout the duration of the study;
- Administration of any nonsteroidal anti-inflammatory drugs (NSAIDs) including but not limited to topical, systemic (including sleep-aids containing NSAIDs), inhaled, or irrigation solution at least 1 week before surgery and throughout the duration of the study, with the exception of aspirin, where oral doses of 165 mg/day or lower are allowed;
- Ocular or systemic antihistamines (including sleep-aids containing an antihistamine), or mast cell stabilizers in either eye at least 1 week before surgery and throughout the study's dosing period;
- Triamcinolone in either eye at least 90 days before surgery and throughout the study's dosing period;
- Medications used to treat benign prostatic hyperplasia throughout the duration of the study;
- Inhaled, ingested, sublingual, transdermal or topical products containing marijuana, tetrahydrocannabinol (THC) or cannabidiol (CBD) at least 1 week before surgery and throughout the study's dosing period and for one day after the study's dosing period ends;
- Systemic pain relievers, analgesics (e.g., pregabalin, gabapentin, opioids) 14 days before surgery and throughout the duration of the study;
- Any supplement, prescribed medication or over-the-counter product that the investigator feels may interfere with the study parameters, including homeopathic remedies, analgesics, and pain medication.

During the study dosing period (Day -1 through Day 14), if the investigator determines that a rescue medication is necessary due to lack of efficacy (whether at a planned study visit or at an unscheduled visit), the subject should be discontinued from the study drug and the appropriate rescue medication prescribed. The subject should continue to be seen for all remaining study visits to assess safety and efficacy. This information must be recorded in the subject's source record and on the appropriate eCRF.

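### The secondary pain-score-0 analysis has no rule for rescued subjects, so a subject who is pain-free on rescue medication counts as a success; the Day 14 end of the rescue provision needs a smaller clarification.

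*Combined protocol and SAP*

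**What the plan says.** **Rescue.** Section 7 has one rescue paragraph for lack of efficacy. It begins "During the study dosing period (Day -1 through Day 14), if the investigator determines that a rescue medication is necessary" and directs that study drug be stopped and a suitable rescue drug prescribed, at a planned or unscheduled visit. It then says: "The subject should continue to be seen for all remaining study visits to assess safety and efficacy".

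**Primary endpoint.** Sections 10.2 and 10.6.1 count a subject as a failure if the ACC grade at Day 15 is above 0 or if rescue was used before Day 15.

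**Secondary endpoint.** Sections 10.2 and 10.6.2 compare the proportions with a VAS pain score of 0 at Days 1, 8, 15, 22 and 32, using a two-sided 5% z-test at each visit. Neither section mentions rescue.

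**Disallowed drugs.** Section 7 bars "Any corticosteroid at least 15 days before surgery and throughout the duration of the study"; NSAIDs, including any "irrigation solution at least 1 week before surgery and throughout the duration of the study, with the exception of aspirin" at low oral dose; and "Systemic pain relievers, analgesics (e.g., pregabalin, gabapentin, opioids) 14 days before surgery and throughout the duration of the study". Other items stop earlier, for example "Triamcinolone in either eye at least 90 days before surgery and throughout the study's dosing period". Section 4.1 gives the extent of the study as "throughout the study period (from Screening through Day 32", and Section 2 schedules "3 visits (Day 15, Day 22, and Day 32) during the evaluation phase".

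**The concern.** Rescued subjects stay in follow-up and keep giving VAS scores, some of them recorded while an effective anti-inflammatory or analgesic is working. The primary analysis deals with this by counting rescue as failure. The pain analysis is silent, so the plain reading uses the observed score. A vehicle subject who needed rescue and then became comfortable would count as evidence that vehicle controlled pain.

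At stake is the interpretation of the only secondary efficacy endpoint. If rescue is more frequent on vehicle, the difference is pulled towards zero. The two efficacy endpoints would also treat the same subject in opposite ways, as a failure for inflammation and a success for pain. With no rule written down, the choice could be made after unmasking.

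A smaller matter lies in the same section. Day 15 is the first scheduled examination after the last dose. If an eye is still inflamed or painful then, the written rescue provision has already ended, while the bars on the drugs most likely to be used continue.

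**Working it through.** The plan states no assumed pain or rescue rate and no power, so there is no figure to reproduce. The check is a comparison of rules, followed by arithmetic for scale.

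**1. Rescue rule by endpoint**

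| Endpoint | Visits tested | Rescue rule | Section |
|---|---|---|---|
| ACC grade 0 (primary) | Day 15 | Rescue before Day 15 is failure | 10.2, 10.6.1 |
| Pain score 0 (secondary) | Days 1, 8, 15, 22, 32 | None | 10.2, 10.6.2 |

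The rule is absent at all 5 visits, but the exposure is uneven. Day 1 is the day after surgery, so only very early rescue could affect it. Days 8 to 32 are where it matters.

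**2. Weight of one subject**

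Section 2 gives 40 subjects per arm. If all 40 are in the ITT set, one subject moves an arm's proportion by 1/40 = 0.025, or 2.5 percentage points.

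**3. Illustration with assumed counts**

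z = (a − b)/40 ÷ √[p(1 − p) × 2/40], where a and b are the success counts on SURF-201 and vehicle and p = (a + b)/80.

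Worked case, 28 v 18: p = 46/80 = 0.575; standard error = √(0.575 × 0.425 × 0.05) = 0.1105; z = 0.25/0.1105 = 2.26; two-sided p-value 0.024.

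The second column counts rescued subjects as failures. The last two count some of them as pain-free successes.

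| Case | Rescue = failure | Rescued successes added | Observed scores |
|---|---|---|---|
| 1 | 28 v 18, 25 points, p = 0.024 | 2 vehicle | 28 v 20, 20 points, p = 0.068 |
| 2 | 28 v 18, 25 points, p = 0.024 | 4 vehicle | 28 v 22, 15 points, p = 0.166 |
| 3 | 24 v 14, 25 points, p = 0.025 | 2 vehicle | 24 v 16, 20 points, p = 0.074 |
| 4 | 32 v 22, 25 points, p = 0.017 | 2 vehicle | 32 v 24, 20 points, p = 0.051 |
| 5 | 28 v 16, 30 points, p = 0.007 | 4 vehicle, 1 active | 29 v 20, 22.5 points, p = 0.039 |
| 6 | 28 v 16, 30 points, p = 0.007 | 8 vehicle, 2 active | 30 v 24, 15 points, p = 0.15 |
| 7 | 28 v 14, 35 points, p = 0.002 | 2 vehicle | 28 v 16, 30 points, p = 0.007 |
| 8 | 28 v 14, 35 points, p = 0.002 | 4 vehicle | 28 v 18, 25 points, p = 0.024 |

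The test result changes in cases 1 to 4 and 6 but not in 5, 7 and 8. Cases 1 to 4 start close to the 5% threshold and add rescued subjects to vehicle only. The table shows that the rule can matter; it does not estimate how much it will.

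**4. Rescue window against the bars**

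The rescue provision ends at Day 14; the corticosteroid, NSAID and systemic analgesic bars run to Day 32. Two of the five post-surgical visits (Days 15 and 22) fall after the provision ends and before the final visit. The drug list ends some bars with the dosing period and others with the study, so the two periods are distinct. Section 9 directs the investigator to give appropriate medical treatment and applies throughout the study. Section 3 otherwise allows a deviation without prior IRB approval only for an immediate hazard. No clause says that treatment under Section 9 lifts the Section 7 bars.

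**The case against.** **Pain analysis.** Using observed scores regardless of rescue is a coherent treatment-policy strategy, and keeping rescued subjects in efficacy follow-up fits it. If rescue is more frequent on vehicle, it is also conservative, which is tolerable for a Phase 2 secondary endpoint. This stands as far as it goes: either strategy is defensible. But the plan names neither, and the one implied by silence contradicts the rule chosen for the primary endpoint.

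Counting rescue as failure has a cost of its own. A subject rescued early for inflammation alone, and never in pain, would be a pain failure as late as Day 32. That is a reason to report both analyses.

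**Rescue window.** The Day 14 limit fits the paragraph's instruction to stop study drug, which has meaning only during dosing. The paragraph does not expressly lift the drug bars for Days -1 to 14 either, yet it is naturally read as doing so; Section 9 could be read the same way afterwards. This largely stands, and it is why the window is only a clarification.

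A reader might infer that subjects with persisting inflammation or pain after Day 14 cannot be treated. Section 9 contradicts that. A reader might also infer that treating them costs per-protocol membership. Section 10.3 removes only major deviations, the plan does not say whether this treatment would be one, and Section 10.6 names no per-protocol efficacy analysis.

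**Conclusion.** The pain-score-0 endpoint lacks a rescue rule, and as written it counts a rescued subject who scores 0 as a success. This should be settled before unmasking. The size is 2.5 percentage points per such subject, assuming 40 per arm in the ITT set. The bias is towards no difference if rescue is more frequent on vehicle, which is plausible but is not stated in the documents. The total effect cannot be estimated. It would be wrong to read the illustrated p-values as a forecast that the secondary result will be lost: the counts are assumed, and several sets stay significant.

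The mismatch between Day 14 and Day 32 is real but minor. As the plan stands it does not touch the Day 15 primary analysis, and the documents give no rate from which to count affected subjects.

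**What to change.** **Main change, Sections 10.2 and 10.6.2.** State that a subject who received rescue medication before a given visit's VAS assessment is a failure for pain score 0 at that visit and at all later visits. Report observed scores regardless of rescue as a sensitivity analysis.

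**Clarification, Section 7.**
- Run the rescue paragraph through Day 32, with study drug stopped if it is still being dosed.
- State that rescue under it is an exception to the disallowed list and not a protocol deviation.
- Where clinically possible, give rescue after that visit's ACC and VAS assessments.

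**Consequential change, Sections 10.2 and 10.6.1.** Once rescue is allowed after Day 14, it could start on Day 15, or at an unscheduled visit before a late Day 15 examination, and the present cut-off would miss it. Define primary failure by rescue before the Day 15 visit's ACC assessment.

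**Cost.** A wording amendment with IRB approval and one extra sensitivity table; no added visits, subjects or examinations. Rescue already has to be recorded on the eCRF; the record must also show whether it came before or after that day's assessments. Some Day 22 and Day 32 observations will be made after rescue, and a subject rescued early for inflammation alone will count as a later pain failure in the main analysis.
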